## 9 Safety Analysis

Treatment emergent AEs are defined as events that start on or after the first treatment date. Events occurring following the start of treatment which were also reported before treatment began with no change in severity or causality will however not be considered treatment emergent.

AEs will be tabulated according to the current version of the MedDRA. Frequencies and percentages will be presented by product group and overall, for each system organ class, and for each preferred term. Summaries of treatment-emergent AEs, treatment-related treatment-emergent AEs, AEs leading to discontinuation, and serious AEs will be completed.

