Subjects who meet all the inclusion/exclusion criteria will be randomised to one of three treatment groups: test product/positive control, test product/no treatment or positive control/no treatment at the baseline visit. Product application within treatment group will be further randomised to either the right or left side of the face.

Diary Cards will be provided and reviewed at each site visit by the Investigator or designee to confirm and encourage subject compliance. Subjects will be required to

TM Simple Kind to Skin Moisturising Facial Wash is a trademark of Unilever.

Document Name	Clinical Protocol 207468.doc		
Type	Version	Document Identifier	Effective Date
eldo_controlled	3.0; Most-Recent; Effective; CURRENT	090032d580d15804	24-Mar-2017 07:31:33
Reason For Issue	Auto Issue		

complete the diary card every day to record application of test and study cleanser products.

Subjects will be instructed to apply each test product to the assigned side of the face, as applicable, (approximately 2 mg / cm²) twice-daily (morning and evening, approximately 8-12 hours apart), for 4 weeks (28 days). Subjects will return to the site on Day 15 (Visit 3) and 29 (Visit 4) without applying the test product at home that morning.

After randomisation, subjects who consent will have high resolution images taken on the left and right side of their face. Instrumental measures will follow in the following order: DermaTOP (Periocular / Crow's Feet Area), TEWL (Sub-ocular/ Cheek Area); Corneometer (Sub-ocular/ Cheek Area); Cutometer (Sub-ocular/ Cheek Area). The same schedule of events (except randomisation and high resolution photos) will be repeated for Day 15 (Visit 3). Day 29 (Visit 4) will be a repeat of Visit 2 (Day 1) (except randomisation).

Prior to all instrumental measurements and clinical assessments, subjects will be acclimatised in a controlled environment (temperature 20-22°C, relative humidity between 40-60%) for a period of at least 30 minutes [EEMCO, 1997].

On Day 1 (Visit 2) and Day 15 (Visit 3) on-site application of product will be supervised by the study site staff and will be performed only after the clinical and instrumental measurements are completed.

After the study has completed, all of the high resolution images will be evaluated by blinded lay persons to rank the appearance of texture.

Visit 1 - Screening / Washout Visit

1. Informed consent
2. Demographics
3. Medical History
4. Current / Concomitant medication

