9. High Resolution Photos for Texture Assessment (Appendix 4)
10. DermaTOP Assessment
11. TEWL Assessment
12. Corneometer Assessment
13. Cutometer Assessment
14. Test Product(s) Dispensing
15. Supervised Test Product Application

Visit 3- Day 15 (Week 2)

The following assessments will be conducted in the order written:

1. Current / Concomitant medication
2. Adverse Events
3. Diary Review (Compliance)
4. Continued Eligibility

Document Name	Clinical Protocol 207468.doc		
Type	Version	Document Identifier	Effective Date
eldo_controlled	3.0; Most-Recent; Effective; CURRENT	090032d580d15804	24-Mar-2017 07:31:33
Reason For Issue			Auto Issue

5. Clinical Fitzpatrick Wrinkle Score (Appendix 3)
6. DermaTOP Assessment
7. TEWL Assessment
8. Corneometer Assessment
9. Cutometer Assessment
10. Supervised Test Product Application

Visit 4 – Day 29 (Week 4)

The following assessments will be conducted in the order written:

1. Current / Concomitant medication
2. Adverse Events
3. Diary Review (Compliance)
4. Continued Eligibility
5. Clinical Fitzpatrick Wrinkle Score (Appendix 3)
6. High Resolution Photos for Texture Assessment (Appendix 4)
7. DermaTOP Assessment
8. TEWL Assessment
9. Corneometer Assessment
10. Cutometer Assessment
11. Test Product, Study Cleanser and Diary Return
12. Subject Discharge from Study

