7.1.1. Adverse Events

The investigator or site staff will be responsible for detecting, documenting and reporting events that meet the definition of an AE or SAE.

Adverse Event Definition:

- An AE is any untoward medical occurrence in a patient or clinical investigation subject, temporally associated with the use of an investigational or washout product, whether or not considered related to the investigational or washout product.
- NOTE: An AE can therefore be any unfavourable and unintended sign (including an abnormal laboratory finding), symptom, or disease (new or exacerbated) temporally associated with the use of an investigational or washout product.

Events meeting AE definition include:

- Any abnormal laboratory test results (if applicable) or other safety assessments, including those that worsen from baseline, and felt to be clinically significant in the medical and scientific judgment of the investigator.
- Exacerbation of a chronic or intermittent pre-existing condition including either an increase in frequency and/or intensity of the condition.
- New condition(s) detected or diagnosed after study product administration even though it may have been present prior to the start of the study.
- Signs, symptoms, or the clinical sequelae of a suspected interaction.
- Signs, symptoms, or the clinical sequelae of a suspected overdose of either study product or a concomitant medication (overdose per se will not be reported as an AE/SAE).

Events NOT meeting definition of an AE include:

- Any clinically significant abnormal laboratory findings (if applicable) or other abnormal safety assessments which are associated with the underlying disease, unless judged by the investigator to be more severe than expected for the subject's condition.
- The disease/disorder/ condition being studied or expected progression, signs, or symptoms of the disease/disorder being studied, unless more severe than expected for the subject's condition..
- Medical or surgical procedure (e.g., endoscopy, appendectomy): the condition that leads to the procedure is an AE.
- Situations where an untoward medical occurrence did not occur (social and/or convenience admission to a hospital).
- Anticipated day-to-day fluctuations of pre-existing disease(s) or condition(s) present or detected at the start of the study that do not worsen.

Document Name	Clinical Protocol 207468.doc		
Type	Version	Document Identifier	Effective Date

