7.2. Recording Adverse Events and Serious Adverse Events

Recording of adverse events and serious adverse events:

- The investigator or site staff will be responsible for detecting, documenting and reporting events that meet the definition of an AE or SAE.
- The investigator or site staff will then record all relevant information regarding an AE/SAE in the CRF.
- There may be instances when copies of medical records for certain cases are requested by GSK. In this instance, all subject identifiers, with the exception of the subject number, will be blinded on the copies of the medical records prior to submission to GSK.
- The investigator will attempt to establish a diagnosis of the event based on signs, symptoms, and/or other clinical information. In such cases, the diagnosis will be documented as the AE/SAE and not the individual signs/symptoms. Clinical AEs will be described by diagnosis and not by symptoms when possible (e.g., upper respiratory tract infection, seasonal allergy, etc. instead of runny nose).
- AEs will be collected from the start of the washout product and until 5 days following last administration of the study product.
- SAEs will be collected over the same time period as stated above for AEs. However, any SAEs assessed as **related** to study participation (e.g., investigational product, protocol mandated procedures, invasive tests, or change in existing therapy) or related to a GSK concomitant medication will be recorded from the time a subject consents to participate in the study up to and including any follow-up contact.
- Medical conditions reported prior to the time period for reporting AEs/SAEs should be recorded as part of the subject's medical history.

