9.3.4. Safety Analysis(es)

Adverse Events (AE) will be tabulated according to the current version of the Medical Dictionary for Regulatory Activities (MedDRA). Frequencies and percentages will be presented by treatment arm overall, for each system organ class,

Document Name	Clinical Protocol 207468.doc		
Type	Version	Document Identifier	Effective Date
eldo_controlled	3.0; Most-Recent; Effective; CURRENT	090032d580d15804	24-Mar-2017 07:31:33
Reason For Issue		Auto Issue	

and for each preferred term. Summaries of treatment-emergent AE's, treatment-related AEs, AEs leading to discontinuation, and serious AEs will be completed.

Document Name	Clinical Protocol 207468.doc		
Type	Version	Document Identifier	Effective Date
eldo_controlled	3.0; Most-Recent; Effective; CURRENT	090032d580d15804	24-Mar-2017 07:31:33
Reason For Issue	Auto Issue		

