### Section: 9 Safety Analysis

**Reason for amendment:** Reference to additional pre-unblind step of assigning application site(s) AE's to treatment at that site(s).

**Original text:** Treatment emergent AEs are defined as events that start on or after the first treatment date. Events occurring following the start of treatment which were also reported before treatment began with no change in severity or causality will however not be considered treatment emergent.

AEs will be tabulated according to the current version of the MedDRA. Frequencies and percentages will be presented by product group and overall, for each system organ class, and for each preferred term. Summaries of treatment-emergent AEs, treatment-related treatment-emergent AEs, AEs leading to discontinuation, and serious AEs will be completed.

**Amendment:** Treatment emergent AEs are defined as events that start on or after the first treatment date. Events occurring following the start of treatment which were also

Document Name	SAP Amendment 207648.doc		
Type	Version	Document Identifier	Effective Date
eldo_clinical_doc	1.0; CURRENT; Most-Recent; Effective	090032d580d54792	12-Jun-2017 07:04:24
Reason For Issue	Auto Issue		

reported before treatment began with no change in severity or causality will however not be considered treatment emergent.

AEs will be tabulated according to the current version of the MedDRA. Frequencies and percentages will be presented by product group and overall, for each system organ class, and for each preferred term. Summaries of treatment-emergent AEs, treatment-related treatment-emergent AEs, AEs leading to discontinuation, and serious AEs will be completed.

**A further step will take place pre-unblind to flag the AEs by application site if appropriate so that attribution to applied treatment is preserved. This will involve review of all application site AEs and addition of a flag to indicate which site(s) it is applicable to.**

Document Name	SAP Amendment 207648.doc		
Type	Version	Document Identifier	Effective Date
eldo_clinical_doc	1.0; CURRENT; Most-Recent; Effective	090032d580d54792	12-Jun-2017 07:04:24
Reason For Issue	Auto Issue		

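### The treatment-emergent AE rule in SAP section 9 gives no direction of change and uses the date only, so no reading of it sorts washout and Day 1 events correctly

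*SAP*

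**What the plan says.** SAP section 9 defines the term in two sentences. The first admits events by date: "Treatment emergent AEs are defined as events that start on or after the first treatment date". The second removes on-treatment events "which were also reported before treatment began with no change in severity or causality will however not be considered treatment emergent". The SAP amendment to section 9 repeats both sentences unchanged and adds only an application-site step: "A further step will take place pre-unblind to flag the AEs by application site if appropriate so that attribution to applied treatment is preserved". Protocol 9.3.4 names the summary without defining the term: "Summaries of treatment-emergent AE's, treatment-related AEs, AEs leading to discontinuation, and serious AEs will be completed".

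Three parts of the protocol decide which events meet this rule:

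- Section 7.2 opens the collection window before any test product or positive control is used: "AEs will be collected from the start of the washout product and until 5 days following last administration of the study product".
- Section 7.1.1 lists among the events that qualify as AEs: "Exacerbation of a chronic or intermittent pre-existing condition including either an increase in frequency and/or intensity of the condition". Section 7.2 does not say whether worsening of an AE that is already open gets a new record with its own start date.
- Section 3.1 fixes the order of Visit 2. The AE query is step 2, imaging is step 9, the four instruments are steps 10 to 13, dispensing is step 14, and the last step is "15. Supervised Test Product Application". The same section says that on-site application "will be performed only after the clinical and instrumental measurements are completed".

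SAP Appendix 2 lists four AE tables, 9.4.1 to 9.4.4, all limited to treatment-emergent events. SAP section 11 puts 9.4.1 and 9.4.2 in the topline summary.

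**The concern.** A treatment-emergent rule should separate what began or got worse after exposure from what did not. This rule relies on a start date and on whether anything changed, and says neither which way the change must go nor what happens to an open record that worsens. The design makes this matter. Every subject spends the washout on a new cleanser with AE collection already running, and has a Day 1 on which a series of measurements precedes the first application.

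General safety is a stated objective, assessed by AE frequency and severity, and the subjects have self-reported sensitive skin. Tightness that starts on the cleanser and becomes worse on the product side is a relevant tolerability observation. It could be left out of the planned AE tables, while events that improved or that came before exposure could be counted. Two programmers working from the same data could also produce different tables.

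**Working it through.** The plan states no figure on this point, so the check is to apply the two sentences to the kinds of event that the protocol allows.

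**Readings.** *Literal:* an event counts if its start date is Day 1 or later, unless it was reported before treatment and both severity and causality are unchanged. *Implied:* as above for new events, but the second sentence also brings in any prior event whose severity or causality changed, whatever its start date. The last column applies the definition proposed under the fix.

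| Event | Literal | Implied | Proposed |
|---|---|---|---|
| 1. Washout AE (Day -2), one record, worsens on product | No | Yes | Yes |
| 2. Same worsening entered as a new record on Day 5 | Yes | Yes | Yes |
| 3. Washout AE, one record, improves | No | Yes | No |
| 4. Washout AE recurs on Day 5, milder | Yes | Yes | No |
| 5. Washout AE recurs on Day 5, only causality changed | Yes | Yes | Only if it became product-related |
| 6. Washout AE recurs on Day 5, unchanged | No | No | No |
| 7. Day 1 AE, starts before application, not reported at the query, does not worsen | Yes | Yes | No |
| 8. Day 1 AE, reported before application, unchanged | No | No | No |
| 9. Day 1 AE, reported before application, then milder | Yes | Yes | No |

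**What the table shows.**

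- Rows 1 and 2 describe the same clinical course. Under the literal reading the answer depends only on how the site entered it, and protocol 7.2 does not settle that.
- Rows 1 and 3 pull against each other. The implied reading repairs row 1 but then counts the improving event in row 3. The literal reading handles row 3 properly but loses row 1.
- Rows 4 and 9 are counted under both readings because a fall in severity is a change. Row 5 shows the same gap for causality, where a move away from product-relatedness would also count.
- Row 7 is counted under both readings because the first sentence compares dates, and Day 1 before application is the same date as first treatment. Row 8 limits this: an event already reported before application and unchanged afterwards is properly removed.

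**The case against.** The strongest reply is that the second sentence, by exempting only unchanged events, plainly intends changed ones to count, and that protocol 7.1.1 makes an exacerbation an AE in its own right, with an onset on product that satisfies the first sentence. On that view nothing that worsens is lost. This stands in part: the omission needs both the literal reading and a single record that keeps its washout start date. But neither document requires a new record, and the implied reading brings in improving events.

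The Day 1 window is also narrow. The AE query comes first, so what remains is mainly an event arising between query and application. Protocol 7.3 requires causality assessment to consider timing relative to the product, so such an event should seldom reach the treatment-related tables 9.4.2 and 9.4.4. No bias between arms is shown, since the event precedes exposure on either side of the face. That stands, and it is why this part is secondary.

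A reader might infer that a worsened washout event would vanish from all safety reporting. The documents do not support that. SAP section 9 also promises summaries of AEs leading to discontinuation and of serious AEs, neither worded as treatment-emergent only. Protocol 9.3.4 promises treatment-related AEs without that limit, and SAP Appendix 2 provides for the standard listings. What is exposed is the set of four listed AE tables.

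**Conclusion.** The point holds as a defect in a stated rule: neither reading of SAP section 9 classifies all the cases correctly. Omission of a worsened washout event is conditional on the literal reading and one retained record. Counting of milder recurrences occurs under either reading, and counting of continuing events that improve occurs under the implied one. The Day 1 problem is real but small. The primary endpoint is not touched.

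The number of events affected cannot be estimated from the documents, which give no rate of washout or Day 1 events. A reader might try to size it by assuming that 5% to 15% of the 72 randomised subjects have an event ongoing at first application: 72 × 0.05 = 3.6 and 72 × 0.15 = 10.8, or about 4 to 11 subjects. That rate is purely an assumption. The result counts subjects with an event that the rule has to sort, not misclassified events, because those that stay unchanged are handled properly. It should not be quoted as the size of the error, and no lost safety signal is demonstrated.

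**What to change.** Replace the two sentences in SAP section 9 with a definition on these lines. A treatment-emergent AE is either:

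- (a) an event with onset after the first product application, and not present or reported before it; for onsets on Day 1, a before/after application flag decides; or
- (b) an event present or reported before first application, whether ongoing or recurring, that afterwards increases in severity or becomes product-related.

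Prior events that are unchanged or milder afterwards are not treatment-emergent. Part (a) has to exclude recurrences of prior events; otherwise a milder recurrence would be admitted by its onset date and excluded by its severity at the same time.

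In protocol 7.2 or the CRF completion instructions, state that worsening after first application is entered as a new AE record with its own onset date.

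The cost is two sentences in the SAP, one CRF flag and a completion instruction, with no added visit or procedure. The amendment already plans a review of application-site AEs before unblinding, and the Day 1 flag can be checked for those events in that review.

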## 10 Interim Analysis

Not Applicable

Document Name	Statistical Analysis CCI	207468.docx	
Type	Version	Document Identifier	Effective Date
eldo_clinical_doc	1.0; CURRENT; Most-Recent; Effective	090032d580d23463	10-Apr-2017 13:34:23
Reason For Issue	Auto Issue		

## 11 Topline Summary

The following tables will be produced for the topline summary:

Table No.	Description
9.1	Subject Disposition by Treatment Group – All Screened Subjects
9.3.1.1	Summary of DermaTOP Parameter R a at 4 weeks – ITT Population
9.3.1.2	Analysis of DermaTOP Parameter R a – Change from baseline at 4 weeks – ITT Population
9.4.1	Treatment-Emergent Adverse Events – Safety Population
9.4.2	Treatment-Emergent Treatment-Related Adverse events – Safety Population

## 12 Changes to Planned Analysis

There are no changes to the protocol-planned analyses.

## Appendix 1 Study Schedule

Document Name	Statistical Analysis CCI	207468.docx		
Type	Version		Document Identifier	Effective Date
eldo_clinical_doc	1.0; CURRENT; Most-Recent; Effective	090032d580d23463	10-Apr-2017 13:34:23	
Reason For Issue	Auto Issue			

Procedure/ Assessment	Visit 1 Day -3	Visit 2  Day 1	Visit 3  Day 15 (+/- 24 hrs)	Visit 4  Day 29 (+/- 24 hrs)
	Screening / Washout	Baseline Treatment	Week 2 Treatment	Week 4 Treatment
Informed consent	X			
Demographics	X			
Medical History	X			
Current / Concomitant medication	X	X	X	X
Adverse Events		X	X	X
Fitzpatrick Skin Type Assessment (Appendix 2)	X			
Diary Review (Compliance) 		X	X	X
Continued Eligibility		X	X	X
Clinical Fitzpatrick Wrinkle Score in Periocular / Crow's Feet Area (Appendix 3) 	X	X	X	X
Inclusion / Exclusion Criteria	X	X		
Subject Eligibility 	X	X		
Study Cleanser and Diary Dispensing	X			
Randomisation 		X		
USR- CliP High Resolution Images Left and Right Side of Face 		X		X
DermaTOP Measurement  Periocular / Crow's Feet Area		X	X	X
TEWL Measurement  in Sub-ocular/ Cheek Area		X	X	X
Corneometer Measurement  in Sub-ocular/ Cheek Area		X	X	X
Cutometer Measurement  in Sub-ocular/ Cheek Area		X	X	X
Test Product(s) Dispensing		X		
Supervised Test Product Application		X	X	
Test Product, Study Cleanser and Diary Return				X
Subject Discharge from Study				X

1. On the day of site visit, subjects will be instructed to cleanse their face in the morning with tap water only and not to apply the test product or control. Measurements and assessments will be performed at least 12 hours after the last application of test products.
2. Subjects to be randomised to one of three treatment groups: test product/positive control, test product/no treatment or positive control/no treatment at the baseline visit.
3. Subjects will be acclimatized in a controlled environment (temperature 20-22°C, relative humidity between 40-60%) for a period of at least 30 minutes before the clinical and instrumental assessments are performed (EEMCO, 1997).
4. Diary to be reviewed by investigator or designee to confirm and encourage subject compliance.
5. At the end of the study, a blinded lay panel will assess all of the high resolution images for Texture by texture ranking (Appendix 4).
6. Inclusion criteria 7b to be reviewed at Screening and Baseline.
7. A 30 minute waiting time will occur in an acclimatized room after the USR-CliP High Resolution Images.

Document Name	Statistical Analysis CCI	207468.docx	
Type	Version	Document Identifier	Effective Date
eldo_clinical_doc	1.0; CURRENT; Most-Recent; Effective	090032d580d23463	10-Apr-2017 13:34:23
Reason For Issue	Auto Issue		

